4.1. General Principles

Descriptive statistics (mean, standard deviation, median, range, etc.) will be used to summarize continuous variables, and counts and proportions will be used to summarize categorical variables by treatment group. For time-to-event variables, Kaplan-Meier method will be used to estimate the survival function and estimate the median survival time and its 95% confidence interval, and survival curves will be provided.

Unless otherwise specified, the cycle baseline measurement for Cycle 1 is defined as the last available valid measurement within 7 days before the start of study medication on Cycle 1 Day 1; the baseline measurement for subsequent cycles is defined as the last available valid measurement within 3 days before the start of study medication on Cycle 1 Day 1. Unless otherwise specified, study baseline measurements are defined as the last available valid measurement prior to the first dose of study drug. If the last valid measurement coincides with the start date of the first study drug administration, the measurement will be considered as baseline measurement. Adverse events or concomitant medications that occurred on the day of the first dose of study drug are considered postbaseline.

The start date of each cycle is defined as the first day of the cycle, i.e., the date of the first study drug administration of the cycle; the end date of each cycle is defined as the start date of the next cycle, or the first day of the cycle +36 days if the next cycle is not entered.

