4.4.2.4. Total occurrence of major adverse hematologic event

Major adverse hematologic event (MAHEs) are composite endpoints to assess the effect of Trilaciclib. MAHE consists of the following 5 component events:

- Involved hospitalization
- Leading to chemotherapy dose reduction
- Febrile neutropenia
- Extended SN (greater than 5 days)
- RBC transfusion occured on/after Week 5.

The total number of events for each MAHE component is the sum of the number of events that occurred on the date of first study drug administration and before the end of the last treatment cycle. The total number of events for MAHEs during treatment is the sum of the number of events for each MAHE component. For patients who does not experience any MAHE, the total number of MAHE events is 0.

MAHEs will be coded using the most current version of MedDRA and the total number of MAHEs, duration of treatment (weeks), weekly event rates, and cumulative event rates every 3 weeks will be summarized by number of lines of treatment. According to the actual MAHEs, the above summaries will be repeated separately by component events , but for MAHE component events leading to chemotherapy dose reduction and SN prolongation, the cumulative

event rates will be summarized by cycle rather than every 3 weeks. Part 2 of the study will also analyze the adjusted rate ratio between the Trilaciclib and placebo groups using a negative binomial regression model. The model includes the three IRT-based randomization stratification factors and treatment group as fixed effects, and the log-transformed values of treatment duration (weeks) or cycle number as offset variables. Two-sided P values, aRR (Trilaciclib versus placebo) and their 95% CIs will be provided. Cumulative incidence of MAHEs within specified subgroups will be presented using forest plots.

Time to first onset (months) for each MAHE component event = (date of first MAHE component event – date of first study drug administration + 1)/30.

For patients who developes MAHEs, the time (months) from the first study drug administration (randomization date in Part II) to the first occurrence of MAHEs will be summarized and Kaplan-Meier curves will be provided. Time to first MAHE refers to the event with the shortest time to first occurrence of the MAHE component; if a patient does not have an MAHE, it will be censored at the end date of the last cycle, date of death, end of study, or last contact date for that patient, whichever cames first.

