4.4.3.1. Absolute neutrophil count trough values by cycle

Absolute neutrophil count (ANC) will be summarized by descriptive statistics for cycle trough values (which are lower than the ANC value at baseline for that cycle) and changes from baseline between the start and end of each cycle. Cycle trough values for ANC will be summarized descriptively for Part II of the study to evaluate confounding effects of G-CSF administration separately by the presence or absence of G-CSF administration during treatment.

4.4.3.2. Absolute neutrophil counts, platelet counts, absolute lymphocyte counts, and hemoglobin over time

Hematology parameters, including ANC, platelet count, absolute lymphocyte count (ALC), and hemoglobin (HGB) will be summarized by treatment group using descriptive statistics based on laboratory hematology results at baseline and each visit time point. Listing will be provided for detials. ANC will be summarized descriptively to evaluate confounding effects of G-CSF administration separately according to the presence or absence of G-CSF administration during treatment.

Time-line plots for mean ANC, platelet count, ALC, HGB, and change from baseline in HGB (with 95% confidence intervals) will be provided by cycle.

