g. Hematology includes: white blood cell (WBC), red blood cell (RBC), hemoglobin (Hb), platelet (PLT), hematocrit (HCT), neutrophil (NEU), eosinophil (EOS), basophil (BAS), monocyte (MON), lymphocyte (LYM), etc.; hematology in Cycle 1 is scheduled on Day 1 (within 24 hours before administration), Day 3, Day 8, Day 10, Day 15, and baseline hematology should be performed within 24 hours before the first study dose; hematology in other cycles is performed on Days 1 and 8 of each cycle, and the examination on Day 1 of each cycle is performed before administration. Subjects were eligible for chemotherapy administration as determined by predose hematology results on Day 1 of each cycle.

Product: Trilaciclib Protocol Number: B02B0)801-TRILA-3	01			Jiangsu S	imcere Pha	armaceutica	l Co., Ltd					
	Saraanin	Treatment Period ^a (21 days per cycle, 6 cycles)											Survival
	g Period		Cycle 1 Cycle 2 and above									Safety Visit ^b	Follow-up ^c
	D-21 ~ - 1	D1	D2	D3	D8	D10	D15	D1	D2	D3	D8	+ 30 days	Every 60 days
Window (Days) ± 1 ± 1 ± 1 ± 3 ± 1 ± 7													

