5.4. Appendix 4 Window Visits

During the treatment cycle, if more than one visit occurred within a window visit, the visit closest to the scheduled date was selected; if the distance between two visits and the scheduled date was the same, the visit occurring later was selected as the window visit; and if multiple visits occurred on the same day, the worst case was selected.

	Cycle 1					Cycle 2 and above			Safety Visit	
Visits	D1	D3	D8	D10	D15	End	D1	D8	End	
Scheduled Date	1	3	8	10	15	22	1	8	22	30 (+ 3)
Biochemistry	-3 to 1		2 to 11		12 to 18	19 to end of cycle	-3 to 1	2 to 15	16 to end of cycle	Date of first dose of last cycle to 40 days after first dose
Hematology	-1 to 1	2 to 5	6 to 9	10 to 12	13 to 18	19 to end of cycle	-3 to 1	2 to 15	16 to end of cycle	Date of first dose of last cycle to 40 days after first dose

|--|

^[a] Relative to Day 1 of each cycle

Product: Trilaciclib Protocol Number: B02B00801-TRILA-301

	Cycle 1					Cycle 2 and above			Safety Visit	
Visits	D1	D5	D10	D12	D15	End	D1	D10	End	
Scheduled Date ^[a]	1	5	10	12	15	22	1	10	22	30 (+ 5)
Biochemistry	-3 to 1				2 to 18	19 to end of cycle	-3 to 1	2 to 16	17 to end of cycle	Date of first dose of last cycle to after first dose 42 days
Hematology	-1 to 1	2 to 7	8 to 11	12 to 13	14 to 18	19 to end of cycle	-3 to 1	2 to 16	17 to end of cycle	Date of first dose of last cycle to after first dose 42 days

Visit Window - 2/3L Subject

^[a] Relative to Day 1 of each cycle

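### SAP 4.1 ties the baseline of every later cycle to Cycle 1 Day 1; as a minor point, 4.4.2.4 does not say how extended SN is timed when later cycles have one mid-cycle ANC

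*SAP*

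**What the plan says.** **Cycle baseline.** SAP 4.1 sets the Cycle 1 baseline as the latest valid value in the 7 days before study drug on Cycle 1 Day 1. The baseline for "subsequent cycles is defined as the last available valid measurement within 3 days before the start of study medication on Cycle 1 Day 1". Two other places treat each cycle as having its own baseline. SAP 4.4.3.1 describes trough values as those "which are lower than the ANC value at baseline for that cycle". Appendix 4 gives hematology from Cycle 2 a Day 1 window of -3 to 1, with the footnote "Relative to Day 1 of each cycle". For Cycle 1, Appendix 2 footnote g says that "baseline hematology should be performed within 24 hours before the first study dose".

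**Extended SN.** MAHE is a key secondary endpoint with five components, one of which is "Extended SN (greater than 5 days" (SAP 4.4.2.4). That section does not say how the length is derived. SAP 4.4.1.1 gives a per-cycle rule: count from the first ANC below 0.5 to the first lasting ANC at or above 0.5, and stop at cycle end if unresolved. SAP 4.4.1 includes unscheduled values and uses actual dates. In the EC schedule, "hematology in other cycles is performed on Days 1 and 8 of each cycle". For topotecan, the table "Visit Window - 2/3L Subject" in Appendix 4 has Days 1 and 10 from Cycle 2.

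**The concern.** A programmer who follows 4.1 as written would compute ANC changes in later cycles from a value taken before Cycle 1. Those changes would mix incomplete recovery since Cycle 1 with the fall within the cycle. A value lying between the two candidate baselines would be a trough under one rule and not under the other.

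The second point is about what a component measures. With one mid-cycle ANC, the schedule rather than the patient largely fixes the recorded SN length from Cycle 2. Cycle 1 has several mid-cycle ANCs and can record short episodes. The negative binomial rate ratio and the time to first MAHE pool all cycles, so they combine a coarse duration in Cycle 1 with something close to any SN seen on Day 8 or Day 10 afterwards.

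**Working it through.** The SAP states no figure for either quantity, so there is none to reproduce first.

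**1. Which value does 4.1 select?** Both rules in 4.1 have the same anchor, Cycle 1 Day 1, with windows of 7 and 3 days. Hematology is due within 24 hours before the first dose, so both windows normally select the same value, and every cycle inherits the Cycle 1 baseline. Its nominal age at the start of cycle k is 21 × (k − 1): 21, 42, 63, 84 and 105 days for Cycles 2 to 6.

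**2. Error in a later-cycle change.** (trough − ANC at C1D1) − (trough − ANC at CkD1) = ANC at CkD1 − ANC at C1D1. The documents give only a floor of 1.5 × 10^9/L, at entry and in protocol 5.4.2 for redosing. If one assumes 3 to 7 at C1D1 and 1.5 to 5 at a later Day 1, the error runs from 1.5 − 7 = −5.5 to 5 − 3 = +2.0 × 10^9/L.

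**3. Recorded SN length from Cycle 2, no retest, 4.4.1.1 rule.**
- Nominal days: 22 − 8 = 14 (EC); 22 − 10 = 12 (topotecan).
- Over the visit windows: mid-cycle day ±1 (3 values) × next Day 1 on Days 19 to 25 (7) × its ANC 0 to 3 days earlier (4) = 84 combinations. EC runs from 16 − 9 = 7 to 25 − 7 = 18. Topotecan runs from 16 − 11 = 5 to 25 − 9 = 16. None of 84 (EC) and 1 of 84 (topotecan) is 5 days or less.
- Next cycle delayed by 2 weeks: 36 − 8 = 28; 36 − 10 = 26.
- Final cycle, to the safety visit 30 ± 7 days after the last dose: Day 33 (EC) or Day 35 (topotecan), so 33 − 8 = 25 and 35 − 10 = 25 nominally. With both windows the range is 26 − 9 = 17 to 40 − 7 = 33 (EC) and 28 − 11 = 17 to 42 − 9 = 33 (topotecan). If the SN is unresolved at cycle end (Day 1 + 36 days = Day 37), it is closed there: 37 − 8 = 29 or 37 − 10 = 27.
- Cycle 1 for contrast, nominal days: Day 8 to 10 gives 2 and Day 10 to 15 gives 5 (EC); Day 10 to 12 gives 2 and Day 12 to 15 gives 3 (topotecan). Day 15 to 22 gives 7 in both, so Cycle 1 is coarse too.

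**4. Could the component ratio move, and which way?** This is an illustration on assumptions only: onset uniform over a 7-day window, true duration 0.5 day plus an exponential with mean m, no retests, and the SAP 2.2 planning rates of 10% and 45% borrowed for later cycles. If the mid-cycle visit falls L days after the onset window opens:
- P(seen, so recorded as extended) = [0.5 + m(1 − e^(−(L − 0.5)/m))]/7
- P(truly over 5 days) = e^(−4.5/m)

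With onset on Days 5 to 12, L = 3 (EC) or 5 (topotecan):
- Same onset and duration in both arms: 0.10/0.45 = 0.22, true and recorded.
- m = 2 on trilaciclib, 6 on placebo: true 0.22 × 0.105/0.472 = 0.05; recorded 0.22 × 1.93/2.54 = 0.17 (EC) and 0.22 × 2.29/3.67 = 0.14 (topotecan). The apparent effect is diluted.
- m = 4 in both, onset 2 days later on trilaciclib: true 0.22; recorded 0.22 × 0.97/2.36 = 0.09 (EC) and 0.22 × 2.36/3.20 = 0.16 (topotecan). The apparent effect is exaggerated.

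The direction therefore depends on inputs that the documents do not give.

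**The case against.** **Baseline.** This reads as a slip. The 3-day window in 4.1 matches the Day 1 window in Appendix 4, so the intended anchor can be recovered. That is fair, but 4.1 is the operative definition and a literal reading gives wrong values. A reader might infer that the primary analysis inherits the error. It does not: the model in 4.4.1.1 uses the study baseline ANC, which 4.1 defines separately.

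**Extended SN.** The arithmetic above describes an extreme, and most of this objection stands.
- Unscheduled ANCs are included (SAP 4.4.1), and protocol 7.2.1 permits extra tests. Protocol Table 7 separates Grade 4 neutropenia under 7 days from 7 days or more, which scheduled ANCs alone cannot show, so some retesting is likely.
- Over-counting depends on short true durations. Across the onset windows tried (Days 3–10, 5–12, 5–16, 8–16), the largest recorded-to-true ratio without retests is 3.1 (EC) or 3.3 (topotecan) at m = 2, but 0.99 or 1.24 at m = 8.
- Protocol Table 3 gives a rough anchor: placebo mean Cycle 1 DSN of 3, 4 and 7 days with SN in 42.1%, 49.1% and 75.9%, or about 7.1, 8.1 and 9.2 days per affected patient. The means are rounded, and the table does not say whether the SN rates are for Cycle 1 only. On that anchor, many placebo episodes would truly exceed 5 days.
- For SN prolongation the SAP already plans that "event rates will be summarized by cycle rather than every 3 weeks". This shows the pattern but does not change the pooled estimates.
- The two DSN strategies use the same dates for resolved SN. They differ only when SN is unresolved at cycle end or is cut short by death.

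A reader might also infer that the MAHE rate ratio is biased in favor of trilaciclib. The documents do not support that: SN onset, later-cycle SN rates and retest frequency are not given, and the illustration moves both ways.

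**Conclusion.** The baseline rule in SAP 4.1 is wrong as written and conflicts with 4.4.3.1 and Appendix 4. Its reach is limited to descriptive secondary summaries of ANC trough and change in later cycles. The −5.5 to +2.0 range rests on assumed ANC values.

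The extended-SN point is minor. The recorded lengths follow from the schedule under the 4.4.1.1 rule, on the assumption that this rule applies and that there is no retest. Under the same conditions, an SN that falls between visits is missed altogether. What this does to the MAHE rate ratio cannot be established in size or direction, and extended SN is only one of five components. The description of the trough as a value below baseline, rather than the lowest value, is editorial. Cycle 1 DSN and the sample size are unaffected.

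**What to change.** 1. **SAP 4.1:** for cycles after the first, replace Cycle 1 Day 1 with Day 1 of that cycle and keep the 3-day window. This costs one phrase.
2. **SAP 4.4.2.4:** state that extended SN uses the per-cycle DSN of 4.4.1.1, with actual dates and unscheduled ANCs. This costs one sentence.
3. **Optional:** prespecify one MAHE sensitivity analysis (rate ratio and time to first event) that omits the extended-SN component. SAP 4.9 now only allows further analyses as needed. It uses data already collected. The price is fewer events and a changed composite, so it is a robustness check and not a corrected estimate.
4. **Editorial, SAP 4.4.3.1:** define the trough as the lowest post-dose ANC in the cycle.

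None of these changes visits or clinical management.

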4.2. Analysis Set

4.2.1. Myeloprotection efficacy analysis set

Full Analysis Set (FAS): All enrolled patients who received at least one dose of study drug according to the intention-to-treat (ITT) principle. Randomized subjects will be analysized according to the assigned group at randomization. Unless otherwise specified, efficacy analyses for myeloprotection will be based on the FAS.

Per-Protocol Analysis Set (PPS): Patients with major protocol deviations that were judged to have a major impact on the results are excluded from the FAS. PPS is a subset of FAS, and the classification criteria need to be finalized before database lock library. The PPS may be used

Confidential

for analysis of individual myeloprotective efficacy endpoints.

4.2.2. Antitumor Efficacy Analysis Set

Response Evaluable Analysis Set (RES): all patients who took at least one dose of study drug, had measurable disease at baseline, and completed at least one post-treatment tumor imaging assessment. This analysis set will be used for the analysis of anti-tumor efficacy endpoints related to tumor RECIST1.1 assessment.

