10.2. Analysis set

Full Analysis Set (FAS): All enrolled subjects who received at least one dose of study drug according to the intention-to-treat (ITT) principle. Efficacy analyses will be based on the FAS

set unless otherwise specified. The second part, limited to all randomized subjects, will be analyzed according to the randomized treatment group.

Per-Protocol Analysis Set (PPS): Subjects who had major protocol violations and were judged to have major impact on the results were excluded from the FAS. The PPS set is a subset of the FAS set and the exclusion criteria need to be finalized prior to database lock. The PPS may be used for the analysis of individual endpoints.

Response Evaluable Analysis Set (RES): All subjects who took at least one dose of study drug, had measurable lesion at baseline, and completed at least one post-treatment tumor imaging assessment. This analysis set was used for the analysis of efficacy measures according to RECIST assessment of tumors.

Safety analysis set (SS): All subjects who have received at least one dose of study drug. Safety analyses were based on the SS set by actual treatment received.

PK Analysis Set (PKS): All subjects who received at least one dose of the study drug and had at least one valid concentration data of the test components after dosing. Pharmacokinetic analyses will be based on the PKS set.

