10.3.5. Secondary efficacy endpoint analyses

Key secondary efficacy endpoints

Key secondary efficacy endpoints included SN occurrence, occurrence of red blood cell transfusion (on/after Week 5), occurrence of use of granulocyte colony-stimulating factor (G-CSF), composite endpoint - major hematological adverse events, etc. Descriptive statistics will be used for summarization. Descriptive statistics for continuous data will include mean, median, standard deviation and range. Categorical data will provide counts andpercentages, and the differences between groups and their 95% confidence intervals will be estimated.

Other secondary efficacy endpoints

Other secondary efficacy endpoints included the occurrence of grade 3/4 hematologic toxicities, trough absolute neutrophil count at each cycle, absolute neutrophil count, platelet count, absolute lymphocyte count, and hemoglobin over time, occurrence of ESA use, occurrence of recombinant human interleukin-11 use, occurrence of thrombopoietin (TPO) use, occurrence of intravenous or oral antibiotics, occurrence of serious infectious adverse events, occurrence of serious pulmonary infection adverse events, occurrence of febrile neutropenia, occurrence of platelet transfusions (during chemotherapy), objective tumor response rate (ORR), and disease control rate (DCR). Descriptive statistics will be used for summaries. Descriptive statistics for continuous data will include means, medians, standard deviations, and ranges, and categorical data will provide counts and percentages.

Detailed analysis methods for key secondary efficacy endpoints and other secondary efficacy endpoints will be presented in the SAP.

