4.3. Study Population

4.3.1. Subject disposition

The distribution of patients will be summarized based on all screened patients, including patient screening, enrolled medication, reason for end of treatment, reason for withdrawal from the study and inclusion in each analysis set, and listing will be provided in detail.

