4.5. Anti-tumor efficacy analysis

4.5.1. Objective tumor response rate and disease control rate

A pooled analysis of objective tumor response rate (ORR) and disease control rate (DCR) assessed according to Response Evaluation Criteria in Solid Tumors version 1.1 (RECIST1.1) will be performed based on the Response Evaluation Analysis Set (RES). Based on the assessments at each visit, the number and percentage of patients with best response of CR, PR, SD, PD and NE will be summarized by treatment group when CR/PR confirmation is not required and CR/PR confirmation is required, respectively.

ORR is calculated based on the number of patients with best response of CR or PR. DCR is calculated based on the number of patients with best response of CR, PR, or SD, and 95% CIs for ORR and DCR will be calculated using the Clopper-Pearson method.

ORR as a binary endpoint ("yes"or"no"), CMH weights will be used to analyze the difference in adjusted rates between the two treatment arms (Trilaciclib versus placebo) and their 95% CIs, and 2-sided P values will be calculated based on the stratified exact CMH method.

Waterfall plots of best percentage change from baseline in sum of target lesion diameters, time line plots of change from baseline, and swimming plots of drug exposure and efficacy assessments will be provided for patients based on RES. Supportive data listings will also be provided.

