4.9. Sensitivity Analysis

Sensitivity analyses of myeloprotective endpoints by the presence or absence of concurrent G-CSF cycles will be conducted to support the stability of the analysis results based on the FAS set.

The stability of the primary analysis results (Strategy 1) for Cycle 1 DSNs will be checked by Strategy 2. Additional sensitivity analyses will be performed as needed.

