4.11. Handling of Missing Data

Every effort should be made to minimize the generation of missing data. Missing data will not be imputed unless otherwise specified. For time-to-event endpoints in efficacy, missing data will be handled based on statistical analysis model; for response rate in efficacy (such as ORR, DCR), missing data will be considered as non-responder and included in the analysis.

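### ORR and DCR are planned only for patients with a post-treatment scan, and the SAP's non-responder rule does not say whether treated patients with no scan count

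*SAP*

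**What the plan says.** **Population.** SAP 4.2.2 admits a patient to the RES only with at least one dose, measurable disease at baseline and a post-treatment scan ("completed at least one post-treatment tumor imaging assessment"). Protocol 10.2 sets the same conditions: "had measurable lesion at baseline, and completed at least one post-treatment tumor imaging assessment". SAP 4.5.1 puts ORR and DCR on the RES. The CMH-weighted ORR difference and the stratified exact p-value follow in that section with no other population named.

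**Missing data.** For response rates, SAP 4.11 states that "missing data will be considered as non-responder and included in the analysis". It does not say in which analysis set.

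**Other routes to an all-treated result.** The SAP's FAS default is confined to the myeloprotection endpoints: "Unless otherwise specified, efficacy analyses for myeloprotection will be based on the FAS". The protocol's general FAS default in section 10.2 gives way where another set is specified, and the RES is specified. SAP 4.9 offers only that "Additional sensitivity analyses will be performed as needed".

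**Contrast with PFS.** SAP 4.5.2 analyses PFS, which is also RECIST-based, on the FAS. It censors at randomisation those with no valid post-baseline tumour assessment, so the plan foresees such patients.

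**The concern.** Whether a patient is scanned is decided after randomisation. The first scan is due at week 6 ± 1 (Protocol 7.4). A treated patient who dies, withdraws, is lost or starts new anticancer therapy before any scan drops out of the ORR and DCR denominators. Some of these patients are plausible treatment failures. The reported rates are then at least as high as under non-responder counting in all treated patients. If the arms lose different numbers, the between-arm comparison partly reflects who was scanned.

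The wording of SAP 4.11 adds an ambiguity. Inside the RES it acts only on scanned patients without a usable response, such as those rated not evaluable. If it is meant to bring unscanned patients back, it contradicts SAP 4.2.2 and 4.5.1. Two programmers could reasonably produce different denominators.

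Short-term antitumour efficacy is a secondary objective of Part II, and ORR and DCR are its endpoints. They help to check that marrow protection does not come at the cost of tumour control.

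**Working it through.** **Inputs.** The documents give no figure for ORR, DCR or the number unscanned. The one design figure used here is 40 per arm. SAP 2.2 derives it from 35 per arm and 12% dropout: 70/0.88 = 79.5, rounded up to 80, or 40 per arm. This reproduces the plan. A re-run of its simulation (Poisson means 0.105 and 0.598, 35 per arm, 10,000 trials, two-sided Mann-Whitney-Wilcoxon test) gave 94.9% power against the stated 95% or so. That power concerns the primary endpoint only. The dropout allowance was also made for that endpoint and is not an estimate of the number unscanned. All response and unscanned counts below are assumptions.

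**Effect on one arm.** With n treated, k unscanned and x responders, the RES rate is x/(n-k) and the all-treated non-responder rate is x/n. Their ratio is n/(n-k).
- k = 0: 40/40 = 1.00
- k = 2: 40/38 = 1.05
- k = 5: 40/35 = 1.14

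**Between arms, case (a): unscanned patients are true non-responders.** Take 20 responders of 40 in each arm, so the true ORR difference is 0.

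| Unscanned | RES ORR by arm | RES gap | All-treated gap |
|---|---|---|---|
| 4 vs 4 | 20/36 vs 20/36 | 0 points | 0 |
| 5 vs 3 | 20/35 = 57.1% vs 20/37 = 54.1% | 3.1 points | 0 |
| 6 vs 2 | 20/34 = 58.8% vs 20/38 = 52.6% | 6.2 points | 0 |

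For DCR with 30 of 40 controlled in each arm, 6 vs 2 gives 30/34 = 88.2% vs 30/38 = 78.9%, a gap of 9.3 points. The arm with more unscanned patients looks better.

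**Case (b): unscanned patients would have responded like scanned ones.** With a 50% ORR among the scanned and 6 vs 2 unscanned, the RES gap is 0. All-treated counting gives 17/40 = 42.5% vs 19/40 = 47.5%, a false gap of 5.0 points the other way. For DCR at 75%, it gives 25.5/40 = 63.8% vs 28.5/40 = 71.3%, or 7.5 points.

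**Break-even at 6 vs 2.** Let r be the response rate in scanned patients in both arms and q the rate that unscanned patients would have had.
- True difference: [(34r + 6q) - (38r + 2q)]/40 = -0.1(r - q).
- The RES shows 0, so its error is 0.1(r - q).
- All-treated counting shows -0.1r, so its error is -0.1q.
- The errors are equal in size at q = r/2: 25% when r = 50% (2.5 points each) and 37.5% when r = 75% (3.75 points each).

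Below that value all-treated counting is closer to the truth; above it the RES is.

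**Precision.** At 40 per arm and ORR near 50%, the 95% half-width for a difference is 1.96 × √(2 × 0.5 × 0.5/40) = 0.219, about 22 points.

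**The case against.** The RES is pre-specified, openly named and defined alike in both documents. Choosing between it and the FAS is a choice between two imperfect summaries, and case (b) shows the FAS version misleading where the RES does not. This stands. A reader might infer that the RES should be replaced as the main population. The break-even does not support that, because it turns on the response rate of unscanned patients, which the documents do not give.

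The number unscanned may be small. Inclusion criterion 12 requires expected survival of at least 3 months. Protocol 7.4 keeps scanning patients who stop drug for toxicity and allows earlier scans when clinically indicated. This stands as a limit on size, though it does not remove early deaths, withdrawals or switches of therapy.

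The stakes are modest. ORR and DCR are other secondary endpoints, for which Protocol 10.3.5 says "Descriptive statistics will be used for summaries". PFS and OS use the FAS, so early deaths count there. This also stands, with two qualifications: the SAP adds a stratified ORR difference and p-value, and Protocol 10.3.9 allows exploratory analyses, which PFS and OS are, to be left out of the study report.

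A reader might also infer that all-treated results could never be recovered. The documents do not establish this. SAP 4.3.1 will report "reason for withdrawal from the study and inclusion in each analysis set" with detailed listings, and SAP 4.5.1 promises supportive response listings. Crude rates could be worked out, and perhaps the stratified ones. Planned results are still preferable to reconstructed ones.

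**Conclusion.** The point holds as a gap in the plan and an unclear rule. ORR and DCR are conditional on having been scanned, no FAS version is specified, and SAP 4.11 either fails to reach unscanned patients or contradicts SAP 4.2.2 and 4.5.1.

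Under the assumed counts, the relative excess in one arm is 5% to 14% for 2 to 5 unscanned of 40. The artificial ORR gap runs from 0 points with balanced losses to 6.2 at 6 versus 2, if unscanned patients are non-responders. A gap in the opposite direction is possible under all-treated counting.

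A reader might infer that the plan favours trilaciclib. The documents do not support this: they give neither the number unscanned nor its split by arm, so size and direction in this trial are unknown. Against a half-width of about 22 points no decisive test is at stake, and the primary analysis of Cycle 1 DSN is untouched. The change should be made because it is cheap, not because the plan's conclusions are in danger.

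**What to change.** - **SAP 4.5.1:** add ORR and DCR, with the CMH ORR difference and exact p-value, on all FAS patients with measurable disease at baseline. Count those with no post-baseline scan as non-responders. Inclusion criterion 3 makes this essentially the whole FAS. Report it next to the RES result.
- **SAP 4.11:** state that the non-responder rule applies to this FAS analysis.
- **Reporting:** give the number unscanned, with reasons, by arm beside the ORR and DCR table.
- **RES:** keep it as the protocol-defined analysis and for the waterfall, time-line and swimmer plots.

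**Timing.** Make the change before sponsor personnel are unblinded for the Cycle 1 primary analysis (SAP 4.7). An addition after that could look data-driven.

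**Cost.** SAP wording and some extra tables from data already collected. No protocol amendment is needed, which avoids the Ethics Committee submission that Protocol 11.4 would require; Protocol 10.2 can be aligned if it is next amended for other reasons. The FAS rate will be conservative for patients lost before a scan for reasons unrelated to response. Showing both results lets the reader see how much the choice matters.
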